**Baseline Surveys**: For surveys, ophthalmic technicians will administer the National Eye Institute Visual Function Questionnaire – 9 to patients, which assesses vision-related quality of life. Additional surveys will include: Flint Water- questions are related to living in Flint during the water crisis, Everyday Discrimination Scale, Perceived Stress Scale, UCLA Loneliness Survey, Fall history and Timed Up & Go. They will also administer a standardized survey about socio-demographics and health history. Patients will confirm their address, phone number, and contacts in case of an emergency.

Eyeglasses: After the examination, ophthalmic technicians will help participants who need correction select free (ReSpectacle.org) or low-cost (ZenniOptical.com) eyeglass frames. ReSpectacle.org are donated glasses that have been categorized by exact prescription and are viewable on the website. The organization ships the glasses free- of charge. Participants may also purchase low cost (\$10-\$50) glasses on ZenniOptical.com. On this website, people can choose the frames. For both options, technicians will place the on-line order after the ophthalmologist confirms the eyeglasses prescription remotely, glasses will be shipped to the clinic.

Physician Evaluation: Physician's evaluation will be via a store-and-forward telemedicine technique. This store-and-forward technique, or asynchronous telemedicine, involves the electronic transmission of health data to the provider for evaluation and management. Physicians will review data received within 1 week. The reading ophthalmologist will enter the data into the UM EHR (MiChart). The physician will complete one of two letters with the examination results for the participant indicating whether the participant has ophthalmic disease or not. A time frame for an in-person ophthalmologist examination will be requested if needed. This letter will be sent to the patient via mail and the technician and the patient's PCP (if they have one) via the EHR.

**Physician Review Glaucoma Screen:** In terms of glaucoma screening, a "positive screen" for glaucoma or glaucoma suspect will include the following exam criteria as defined by the TECS protocol:

- 1) Cup to disc ratio  $\geq 0.7$
- 2) Intraocular pressure ≥ 21 mm Hg
- 3) Disc hemorrhage
- 4) Asymmetry of the cup-to-disc ratio by  $\ge 0.2$  where the larger cup-to-disc ratio is  $\ge 0.6$
- 5) Rim thinning or focal notch

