- 6) Abnormal retinal nerve fiber layer observed on OCT defined as >10 microns difference in average retinal nerve fiber layer between the two eyes or the presence of thinning (defined as <5% or yellow) in any of the superior or inferior clock hours)
- 7) Narrow angles on penlight examination or any other concern for narrow angle (complaint of chronic headache or red eye)
- 9) Afferent pupillary defect
- 10) Patient already on treatment or being followed for glaucoma

Physicians will also evaluate for diabetic retinopathy and macular degeneration using validated TECS protocols. If the ophthalmologist identifies an urgent issue such as corneal ulcer, optic disc edema, melanoma, tumor, or retinal vascular event (e.g. central or branch retinal vein or retinal artery occlusion), the physician will contact the patient by phone to arrange immediate care.

Follow-up: The technician will schedule a follow-up visit 4-8 weeks later to give participants their eyeglasses and adjust them. Participants that do not need eyeglasses, but screen positive for eye disease, will return to review their diagnosis letter and management plan and help the patient to schedule an in-person appointment with the ophthalmologist. The ophthalmic technician will help the patient arrange follow-up care and provide educational material to explain diagnoses of cataract, diabetic retinopathy, macular degeneration or glaucoma. (UM Health System Patient Education Clearinghouse at https://pteducation.med.umich.edu/kellogg) If the participant has no need for eyeglasses and has no eye disease, the technician will call the participant to cancel the follow-up appointment after reviewing the ophthalmologist's recommendations. During the follow-up phone call, the satisfaction survey will be administered that would have otherwise been administered at the follow-up visit.

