Glaucoma or glaucoma suspect: Patients with a diagnosis of glaucoma or glaucoma suspect who speak English will be randomized (1:1) to receive standard care as described above, or a 60-minute personalized counseling and education program (intervention) about their diagnosis and the importance of glaucoma follow-up care in maintaining vision (Aim 3)). Ocular hypertension that is low risk for developing glaucoma within one year and/or the recommended follow up time period is one year or more, will not be randomized, the PI will review these cases to determine if they should be randomized or not. Randomization will occur in web-based randomization system. Both groups will be provided support scheduling their ophthalmologist exam and will be asked to complete a brief satisfaction survey. The standard care group will receive a reminder call prior to the ophthalmologist exam, while the intervention will receive a

reminder call as well as a 10-15 minute motivational-interviewing based- counseling follow-up phone call to remind them of why following up for glaucoma care is important to them and trouble-shoot barriers to attending. Further discussion regarding personalized counseling and motivational interviewing can be found later in this protocol. All non-English speaking patients will not be randomized and will receive standard of care education; the personalized counseling is only available in English. We have created a Spanish version of the personalized counseling. Spanish speaking participants will not be randomized, all will receive the personalized coaching session. A Spanish speaking study coordinator will conduct the Spanish eHealth coaching. All subjects participating in the counseling/education encounters will have the option to have their sessions be audio-recorded. Additionally, we will ask English and Spanish speaking participants to complete a visual field test at this appointment. A visual field test measures peripheral vision and is used to review glaucoma patients. This test will take about 20 minutes and there will be no charge to the participant or their insurance. Visual field data will be entered into the REDCap database.

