# Aim 3: Integrate personalized glaucoma education and counseling during the technician visitand test the behavior intervention's impact on adherence to follow-up care with an ophthalmologist.

#### Overall strategy and experimental rigor.

In Aim 3, we will refine and optimize our eHealth-based, personalized education and counseling intervention that improves glaucoma medication adherence to also help support people in prioritizing returning for glaucoma care. This intervention uses a web-based application to generate personalized education materials for patients based on their diagnosis, test results, doctor's recommendations, and barriers to following those recommendations. A glaucoma counselor trained in brief, glaucoma-specific motivational interviewing (MI) uses the

individualized content generated from this web-based application to form the basis of her conversation with the patient. The glaucoma counselor uses MI-based communication strategies – including open-ended questions, reflective listening, and asking permission to give advice – to engage the person in identifying their own barriers to participating in glaucoma follow-up care and brainstorming their own solutions. All patients who screen positive for a diagnosis of glaucoma or glaucoma suspect and are being referred for an in-person examination with an ophthalmologist and who speak English will be randomized to receive either A) a 30-minute session with help scheduling the follow up appointment with an ophthalmologist and an educational hand-out or B) a 60-minute session with help scheduling the follow-up appointment with an ophthalmologist and a personalized counseling and education session about glaucoma. Spanish speaking participants will not be randomized and will receive personalized counseling and education about glaucoma. As of March 2024, Spanish speaking participants will be asked to choose eHealth education or standard education.

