## **Research design-Intervention**

Block randomization: Subjects will be randomized to one of two treatment arms (standard glaucoma education from handouts or personalized education with counseling) in a 1:1 ratio. The time of randomization is when the patient returns for their follow-up visit with the ophthalmic technician. Randomization will occur separately for the two clinics (stratification). A variable-block randomization scheme will be used to assure balanced assignment to the treatment arms throughout the study.

Leveraging eHealth to provide personalized glaucoma education and counseling: The web-based application for personalized glaucoma education has two components woven together into a single tool to support the conversation between the patient and the glaucoma

counselor: 1) an electronic health (eHealth) component and 2) a semi-structured, tailored interview guide to facilitate an MI-based conversation. The eHealth component provides individually tailored disease information and an explanation of a patient's test results. The counselor uses the web-based application on a tablet, to share engaging audio-visual content on a screen. The counselor walks a patient through their diagnosis and test results and what would happen to their vision if glaucoma goes untreated. The counselor then elicits an understanding of what motivates that patient to maintain their vision. The counselor explores what unique obstacles the patient has to engaging in follow-up care. The counselor then assesses the patient's motivation to attend the follow-up appointment. The counselor and patient create a concrete "action plan" that delineates the short-term plan of the steps patient will take to address any identified barriers to follow-up care, which can include addressing motivational factors in a subsequent phone visit if a patient is not interested in follow-up care.

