During the first day of training, counselors are taught to ask open-ended questions, or questions that cannot be answered with a "yes" or "no" response. They learn reflective listening, or para-phrasing what a person has said to ensure the person knows the counselor

is hearing and understanding what they say. They learn to use affirmations to praise actions people are taking towards improving their health and vision. They learn to use the elicit-provide-elicit technique to give information. This involves assessing people's knowledge prior to giving information, asking permission to give new information or advice, and then following up by eliciting the person's response to the new information in order to evaluate their understanding. This non-directive way of giving advice and information supports people's autonomy. During the second day of training, counselors are taught how to make complex reflections.

Complex reflections are statements that para-phrase what a person has said and adds significant meaning to help make a person think about the implications of their statement. Counselors learn how to promote change talk and develop an action plan to adhere to follow-up care recommendations.

Role playing is used to develop these skills using a video collection of glaucoma patients explaining their reasons for not engaging in their glaucoma management. The training consists of approximately 35% didactic material and 65% role-playing and interactive learning.

Primary outcome: The primary outcome will be adherence to the recommended follow-up appointment with the ophthalmologist within 6 months due to availability in scheduling these appointments. Six-month adherence will be used as the endpoint for all participants. Adherence in each treatment group will be calculated as the proportion of patients who attended the initial scheduled follow-up visit with an ophthalmologist as recommended after being diagnosed with glaucoma or glaucoma suspect on screening exam, dividing by the total number of patients diagnosed with glaucoma or glaucoma suspect during the screening exam and scheduled for follow-up with an ophthalmologist. This objective outcome variable will be assessed through record review by the study coordinator who is masked to the treatment allocation.

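### The Aim 3 primary-outcome denominator counts only patients scheduled for follow-up, a step that takes place after randomisation, so randomised patients never scheduled drop out instead of counting as non-adherent

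*Protocol*

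**What the plan says.** The formula is in the primary outcome paragraph of the Aim 3 section Research design-Intervention. Adherence in each treatment group is "the proportion of patients who attended the initial scheduled follow-up visit with an ophthalmologist as recommended", obtained by "dividing by the total number of patients diagnosed with glaucoma or glaucoma suspect during the screening exam and scheduled for follow-up with an ophthalmologist".

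Other sections fix the order of events:

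- **Before randomisation.** The remote ophthalmologist reviews the screening data, and "A time frame for an in-person ophthalmologist examination will be requested if needed" (Ophthalmology Technician Eye Exam, Physician Evaluation). Patients who screen positive for glaucoma or glaucoma suspect and are "being referred for an in-person examination with an ophthalmologist and who speak English will be randomized" (Overall strategy and experimental rigor). Entry depends on referral, not on a booked appointment.
- **Randomisation.** "The time of randomization is when the patient returns for their follow-up visit with the ophthalmic technician" (Research design-Intervention, Block randomization).
- **After randomisation.** At that visit the technician is to "help the patient to schedule an in-person appointment with the ophthalmologist" (Follow-up paragraph). "Both groups will be provided support scheduling their ophthalmologist exam" (Glaucoma or glaucoma suspect paragraph). The control session is described as "a 30-minute session with help scheduling the follow up appointment with an ophthalmologist and an educational hand-out"; the 60-minute intervention session also includes scheduling help, alongside the counselling. The counselling visit closes with a printed action plan that carries the appointment time.

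The Specific Aim/Hypothesis section describes the outcome as a proportion of participants, with no scheduling condition. The Aim 3 Data Analysis section names no denominator.

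**The concern.** A randomised comparison is protected from selection only while each arm's denominator is fixed at or before randomisation. Here the stated denominator is fixed afterwards, inside the session that is being compared. The intervention explores obstacles and motivation to attend, and the protocol foresees a counselled patient who does not want follow-up. Such a patient may never book. Under the stated formula that patient is then removed from the arm, although not getting into care is the failure the intervention is meant to prevent.

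If the arms differ in the share scheduled, the formula compares two selected subsets. The bias can go either way: it can create a difference where none exists, or hide a benefit that comes from getting more people booked. The second possibility bears on how the result is read, because the section Planned Analysis Results Nov. 14, 2023 reports no difference in adherence, randomisation ended on that basis, and the section does not say which denominator was used.

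**Working it through.** **Inputs from the protocol.** 400 participants randomised 1:1, so 200 per arm; the numerator and denominator quoted above. The protocol states no attendance rate, scheduling rate, significance level or power for Aim 3, so there is no figure of its own to reproduce.

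**Exact relation.** For one arm, let A = attended / randomised and s = scheduled / randomised. Everyone in the numerator attended a scheduled visit, so the protocol's proportion is A / s. With I for intervention and C for control:

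RR(protocol) = (A_I / s_I) / (A_C / s_C) = RR(all randomised) × (s_C / s_I)

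This holds whatever the attendance rate.

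**Illustration 1: equal attendance among all randomised.** The true difference is zero, and the protocol's formula shows A/s_I − A/s_C. The scheduling rates, the attendance rates and the two-sided 5% test are assumptions. The last column comes from 400,000 simulated trials with 200 per arm and a pooled two-proportion z test.

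| Scheduled, control / intervention | Factor s_C/s_I | Dropped of 200, control / intervention | Points shown, A = 40% | A = 54% | A = 70% | True null rejected, A = 54% |
|---|---|---|---|---|---|---|
| 95% / 95% | 1.000 | 10 / 10 | 0 | 0 | 0 | 5.0% |
| 90% / 95% | 0.947 | 20 / 10 | −2.3 | −3.2 | −4.1 | 9.5% |
| 85% / 95% | 0.895 | 30 / 10 | −5.0 | −6.7 | −8.7 | 25% |
| 80% / 95% | 0.842 | 40 / 10 | −7.9 | −10.7 | −13.8 | 54% |

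Worked cell: 80% / 95% at A = 54% gives 108/190 = 56.8% against 108/160 = 67.5%, a difference of −10.7 points. With the gaps reversed, the factors are 1.056, 1.118 and 1.188. The all-randomised comparison rejects in about 5% of trials throughout.

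This illustration assumes that the extra scheduled patients in the intervention arm (30 in the last row, 190 − 160) bring no net extra attendance. That is a strong condition.

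**Illustration 2: the intervention works only through scheduling.** Assume 60% attend once scheduled in both arms, with 80% of control and 95% of intervention scheduled.

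- All randomised: 0.60 × 0.80 = 48.0% against 0.60 × 0.95 = 57.0%, a gain of 9.0 points.
- Protocol formula: 60% against 60%, a gain of 0.

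The relation agrees: 57.0/48.0 = 1.1875, and 1.1875 × 0.842 = 1.00.

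**The case against.** The strongest reply is that the phrase is loose prose. Being scheduled for follow-up may simply restate the entry condition of being referred, which is settled before randomisation; on that reading the problem disappears. This is possible and cannot be excluded. But the protocol uses referral for the state at entry and scheduling for the task in the session, and the primary outcome paragraph itself mentions limited scheduling availability and defines attendance by the initial scheduled visit. The words as written favour the literal reading.

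The same paragraph also applies the six-month endpoint to every participant. That sentence sets the time window; the formula that follows still narrows the denominator.

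The design gives scheduling help to both arms, and the later reminder call presumes that an appointment exists. Scheduling may therefore be nearly complete or equal, in which case a true null stays null. This stands: no gap between arms is documented. Equal help does not, however, guarantee equal uptake when only one arm receives motivational counselling. The remark about a patient who does not want follow-up is limited evidence too, since it does not say that the patient goes unscheduled.

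The rejection rates depend on assumed gaps and on extra scheduling yielding no extra attendance. They deserve little weight as forecasts. The exact relation does not depend on them.

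Finally, a statistical analysis plan may define the analysis set. It could do so, but one that analysed all randomised participants would contradict the explicit formula here, so the protocol text needs correcting either way.

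**Conclusion.** The concern holds on the protocol's own wording and should be fixed. The stated formula conditions the primary randomised comparison on an event that follows randomisation and that the assigned session could influence, and no section restores an all-randomised denominator. The distortion of the risk ratio is exactly the control scheduling rate divided by the intervention scheduling rate. For assumed gaps of 5 to 15 points below 95%, that is 0.947 to 0.842, or 1.056 to 1.188 if the gap runs the other way. It is nil if scheduling is equal.

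The actual size is unknown because no scheduling rates are given. Nothing here shows that the reported finding of no difference is wrong; the text leaves the reader unable to tell whether it compares the randomised groups or their scheduled subsets. Confidence is medium, because scheduled may have been meant as referred. The wording in the Specific Aim/Hypothesis section is a summary that names no denominator, so it needs alignment and is not a firm contradiction.

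**What to change.** In the Aim 3 primary outcome paragraph, set the denominator to: *all randomised participants, by assigned arm; a participant who is never scheduled counts as non-adherent.*

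- Leave the numerator as stated (attendance at the initial scheduled visit), and disclose any change to it.
- Report the number and percentage scheduled in each arm, and keep the scheduled-only proportion as a supportive result.
- Align the Aim 3 text in Specific Aim/Hypothesis with this definition. Use a single time window once the three-month statements there and in Aim 3 Data Analysis have been reconciled with the six-month statement in the primary outcome paragraph; that discrepancy is a separate matter.
- If scheduled was meant as referred, with status fixed before randomisation, say so in the paragraph. That alone would resolve the point.
- State which denominator the reported planned analysis used.

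**Cost.** No new data are needed, but the comparison must be re-run and the adherence percentages may fall. The main cost is timing: a planned analysis has been reported and randomisation has stopped, so this is a change to the primary denominator made after a result was known. It must be labelled as such, with both versions shown.

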Aim 3: (Phase 2- HUM 00169371) Integrate personalized glaucoma education and counseling during the technician visit and test the behavioral intervention's impact on adherence to follow-up care with an ophthalmologist. We hypothesize that personalized eHealth education and motivational-interviewing-based counseling will improve adherence to glaucoma follow-up care compared to standard education delivered by a trained staff member. We will test our hypothesis in a randomized controlled trial with participants (n=400) from Aim 2 who have glaucoma or suspected glaucoma. We will make iterative refinements to our existing evidence-based, individualized counseling/eHealth glaucoma education program with a focus on adherence to follow-up recommendations based on learning in Aim 1. The primary outcome is the proportion of participants attending the recommended physician appointments within three months. Secondary outcomes include glaucoma knowledge, satisfaction with communication, and confidence in asking the ophthalmologist questions. Program economic efficiency will be assessed.

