Maintaining Fidelity to Treatment Allocation: All counseling/education encounters will be audio-recorded. A study therapist and MI trainer, will assess a random sample of 10% of encounters (n=40) for fidelity to MI-based counseling. She will be masked to treatment allocation though the personalized counseling sessions will be longer than standard education. She will assess each encounter according to the modified One Pass grading system, a rubric with 17 items that assesses fidelity to MI counseling techniques. Each item is scored on a Likert scale from 1 to 7 and a passing score is set at a mean of 5. Counselors should not be using motivational interviewing-based counseling in the control group and therefore should have an average One Pass score <5 for these participants.

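### The fidelity check assumes every session is recorded although recording is optional, and its control-arm criterion (One Pass average below 5) does not require the arms to differ

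*Protocol*

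**What the plan says.** The paragraph on maintaining fidelity to treatment allocation (Protocol, Aim 3, Research design-Intervention) states "All counseling/education encounters will be audio-recorded". A study therapist who is also an MI trainer "will assess a random sample of 10% of encounters (n=40) for fidelity to MI-based counseling". She uses the modified One Pass rubric of 17 items: "Each item is scored on a Likert scale from 1 to 7 and a passing score is set at a mean of 5". Counselors are not meant to use MI in the control group, and so "should have an average One Pass score <5 for these participants". The rater is described as masked, with the caveat that intervention sessions last longer.

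The earlier paragraph on glaucoma or glaucoma suspect patients (Protocol, Ophthalmology Technician Eye Exam) describes the same encounters differently: "All subjects participating in the counseling/education encounters will have the option to have their sessions be audio-recorded".

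The section Planned Analysis Results Nov. 14, 2023 reports no difference in adherence between coaching and standard education, and ends randomization.

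**The concern.** There are two separate problems.

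1. **Sampling frame.** A random tenth of all encounters can be drawn only if all are recorded. If participants may decline, the draw is from those who agreed. Agreement could differ by arm, because the sessions differ in content and in planned length (30 minutes for control, 60 for intervention).
2. **Control-arm criterion.** The cut of 5 marks when MI has been delivered to a passing standard. A session below it has failed that standard, which is not the same as containing no MI. The protocol's aim for the control arm is that MI is not used there, and a score just under the pass mark does not show that.

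What is at stake is interpretation. After a finding of no difference, readers will ask whether coaching did not improve attendance or whether the two arms received similar counseling. The fidelity ratings are the protocol's direct measure of how much MI each arm received.

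**Working it through.** **Inputs from the protocol.** Planned number randomized, 400 (Aim 3: "We will test our hypothesis in a randomized controlled trial with participants (n=400) from Aim 2 who have glaucoma or suspected glaucoma"); allocation 1:1 ("Subjects will be randomized to one of two treatment arms (standard glaucoma education from handouts or personalized education with counseling) in a 1:1 ratio"); fidelity sample 10%, n=40; 17 items scored 1 to 7; pass mark a mean of 5; control expectation below 5.

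**Assumed, because the protocol gives no figure.** Recorded share c of 90%, 75% or 50%; SD of One Pass session scores of 0.5, 1.0 or 1.5 points.

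**Step 1: the plan's own figure.** 0.10 × 400 = 40. The stated n reproduces, with one encounter per randomized participant and every encounter recorded.

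**Step 2: the frame if recording is optional.**

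| Share recorded | Sessions recorded | 10% of these | 40 as share of recorded |
|---|---|---|---|
| 90% | 360 | 36 | 11.1% |
| 75% | 300 | 30 | 13.3% |
| 50% | 200 | 20 | 20.0% |

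If unrecorded sessions differed from recorded ones by g points on average, the mean of recorded sessions would miss the all-session mean by (1 − c) × g. For g = 1 (assumed) this is 0.10, 0.25 or 0.50 points at 90%, 75% or 50% recorded.

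**Step 3: what the criterion allows.**
- On the 1-to-7 scale, the cut of 5 lies (5 − 1)/(7 − 1) = two thirds of the way up the range. A control arm could sit anywhere below that.
- Read as arm means, intervention 5.0 and control 4.9 meet both expectations, with a separation of 0.1.
- Read session by session, a pass needs an item total of 17 × 5 = 85. A total of 84 gives 84/17 = 4.94, which is below 5. One point on one item separates the two sides of the cut.

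**Step 4: what the ratings can show if compared directly.** A simple draw of 40 from 200 + 200 gives 20 control sessions on average. The SD is √(40 × 0.5 × 0.5 × 360/399) = 3.0, and the hypergeometric 95% range is 14 to 26. With 20 per arm, the 95% half-width of the difference in means is 1.96 × SD × √(1/20 + 1/20) = 0.62 × SD:

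| Assumed SD | Half-width, 20 per arm | Half-width, 10 per arm |
|---|---|---|
| 0.5 | 0.31 | 0.44 |
| 1.0 | 0.62 | 0.88 |
| 1.5 | 0.93 | 1.31 |

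The last column uses 1.96 × SD × √(1/10 + 1/10). It corresponds to half the sessions being recorded and a tenth of those drawn. An uneven 14/26 split costs little: at SD 1.0, 1.96 × √(1/14 + 1/26) = 0.65.

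**The case against.** The strongest reply has four parts.

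- **The conflict over recording may be harmless.** If nearly everyone agreed, the sample is close to a random tenth of encounters. The protocol gives no refusal rate, so the effect cannot be sized, only bounded under assumptions. That is fair, but the two statements still cannot both hold.
- **The control score is an expectation and not a decision rule.** No study-level consequence is attached to it, and the text does not say whether the average is per session or per arm. This stands. A reader might infer that the protocol would certify fidelity on this basis, and the text does not go so far. The weakness of the criterion is the same under either reading of the average.
- **A between-arm comparison may sit in an analysis plan that is not shown.** This also stands, so its absence from the protocol is not counted as a fault. The point rests on the criterion that the protocol does state.
- **Other information bears on separation.** The arms differ by design in session length, in use of the web application and in the extra MI-based call. Aim 3 also lists knowledge, satisfaction with communication and confidence as secondary outcomes. A reader might call the fidelity ratings the only evidence on whether the arms differed, which is too strong. These items show intended differences or downstream effects, however, and none measures MI delivery directly.

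The tempting stronger reading is that the check cannot show that the arms differed. The documents do not support it. The control expectation implies that sessions from both arms are scored, on one scale, and Step 4 shows that a sample of this size can reveal a difference of moderate size.

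**Conclusion.** The point holds in a limited form. The protocol contradicts itself on whether recording is universal, so the fidelity sample can speak only for participants who agreed to be recorded. The single stated control-arm criterion neither requires nor demonstrates separation, and near-identical arms could meet it.

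The ratings themselves remain useful. A direct comparison would have a 95% half-width of about 0.3 to 0.9 points, for an assumed SD of 0.5 to 1.5 and about 20 sessions per arm. These figures use the planned 400 participants. The protocol does not say how many had been randomized when randomization stopped, or how many sessions were recorded. The rater's masking is also imperfect, as the protocol itself notes, because session length differs by arm.

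The fidelity score does not enter the primary outcome, so the primary analysis is unaffected. The matter is minor, and its value lies in helping readers interpret the reported lack of difference in adherence.

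**What to change.** 1. Reconcile the fidelity paragraph with the paragraph on glaucoma or glaucoma suspect patients, so that both say the same about recording.
2. Define the sampling frame as recorded sessions, and report the number and share recorded in each arm.
3. Report the One Pass mean in each arm and the between-arm difference with a 95% CI. State whether the control average is taken per session or per arm.
4. Do not read a control mean below 5, on its own, as absence of contamination. Judge it alongside the difference.
5. Stratify the draw by arm and clinic only if it has not already been made. The protocol does not say whether the ratings are complete, and a fresh draw would then need more rater time.

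Items 1 to 4 cost some wording and one extra table, from ratings already planned.
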